#### 4.3.2.10. Neutralizing Antibodies

Summaries of neutralizing antibody titers will be presented over time by treatment group using descriptive statistics. Antibody titer results will be summarized for each dilution at which 50% neutralization was observed.

The analysis of antibody titers will be performed using the ITT populations.

By-subject data listings will also be provided.

### 4.4. Pharmacokinetic Evaluations

All PK data analysis will be conducted using the PK population.

Maximum plasma concentration (Cmax), minimum plasma concentration (Cmin), and AUC(0-24h) on Days 1, 2, 3, 8, 11 and 14 will be calculated. Plasma PK parameters will be summarized and plotted using descriptive statistics, as appropriate.

### 4.5. Safety Analyses

Safety analyses will be conducted using the Safety population.

#### 4.5.1. Study Drug Exposure

Duration of study drug exposure will be calculated as the number of days subjects were administered study drug and will be summarized for the favipiravir arm using descriptive statistics.

Total drug received (in mg) will be summarized for the favipiravir arm. Percent compliance will be summarized for each subject from the date of first dose through the last dose of study drug per the following definition:

$$\text{Percent Compliance (\%)} = \frac{\text{Actual cumulative amount of drug received (mg)}}{\text{Planned cumulative amount of drug received (mg)}} \times 100\%$$

For subjects who withdrew/discontinued treatment prematurely, the amount of drug planned will be calculated based on the period of treatment up to their withdrawal/termination.

Each Study drug administration per patient will be provided in data listings.

#### 4.5.2. Adverse Events

All AEs will be coded using the MedDRA v23.0 coding system and displayed in tables and data listings using system organ class and preferred term. Missing and partial dates will be handled as described in [Section 3.10.2](#).

Treatment-emergent AEs (TEAEs) will be defined as those occurring coincident with start of treatment through Day 60.

In the favipiravir + SOC arm: Adverse event solicitation and recording will begin immediately following the first dose of favipiravir and will include only on-treatment (treatment-emergent) events. Any changes to a subject's health that occur between the signing of the informed consent and dosing will be recorded as updates to the subject's medical history.

In the SOC alone arm: Adverse event solicitation and recording will begin following the completion of all baseline assessments.

Clinical events related to the progression of COVID-19 will **not** be considered AEs.

Adverse events are summarized by subject incidence rates; therefore, in any tabulation, a subject contributes only once to the count for a given AE in both SOC and preferred term.

The number and percentage of patients with any TEAE, with any TEAE assessed by the Investigator as related to treatment, with any serious TEAE, and with any treatment-emergent serious AE (SAE) potentially related to treatment will be summarized by treatment group and overall.

All AEs occurring on-study will be listed in subject data listings.

By-subject listings also will be provided for the following: subject deaths, SAEs, and AEs leading to treatment/study discontinuation.

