9.2 Sample size justification

Approximately 50 subjects will be enrolled. The primary endpoint analysis will consist of a log-rank test of the difference in treatment groups in the time to viral clearance. Based on a recent publication:

(https://www.sciencedirect.com/science/article/pii/S2095809920300631?via%3Dihub)

it is assumed that the median time to clearance for favipiravir would be approximately 4 days, and the median time for SOC would likely be approximately 11 days; this latter estimate may in fact be conservative since SOC is not as likely to reduce viral load as well as the control in the above referenced study. Using two-sided alpha of 0.10 and power of 90% (appropriate for a trial to be used as the justification for a confirmatory, fully-powered blinded and randomized Phase 3 study), and a fixed per-subject observation period of 15 days, an approximate sample size of 25 subjects per arm (total size of 50) would be required.

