9.7 Safety Analysis

The original exact terms in the electronic data capture (EDC) system used by Investigators to identify AEs other than symptoms of COVID-19 will be fully described and coded according to the Medical Dictionary for Regulatory Activities (MedDRA). Treatment-emergent AEs will be defined as those occurring coincident with start of treatment and through Day 60. TEAEs will be summarized overall and by treatment group and by MedDRA body organ system and preferred term, severity, relatedness, and seriousness.

An overall summary of TEAEs will be presented by treatment, with subject counts and percentages of subjects with the event. This summary will include subjects with any TEAE, any treatment-related TEAE, any serious TEAE, any treatment-related serious TEAE, TEAEs leading to study infusion discontinuation, treatment-related TEAEs leading to study infusion discontinuation, TEAEs leading to death, and treatment-related TEAEs leading to death. The difference in proportions between treatment groups in each of these categories will be calculated.

Summaries of changes over time in laboratory parameters, as well as counts and percentages of laboratory parameters that are Low, Normal, and High compared to the reference ranges will be presented by treatment at each visit and time point. Shift tables will be presented for laboratory parameters with defined severity grades.

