#### 1.1.2. Study Objectives

The primary objective of this study is to determine the effect of favipiravir plus standard of care (SOC) vs SOC on viral clearance.

The secondary objectives of the study are as follows:

- To determine the clinical benefit of administering favipiravir plus SOC compared to SOC alone (assessed using a study-specified 6-point ordinal scale adapted from the

World Health Organization [WHO] Master Protocol [V2.0 24FEB20] COVID-19 7-point ordinal scale) in adult subjects hospitalized with COVID-19.

- To determine if the treatment effect on the 6-point ordinal scale, on Day 15, is reasonably likely to reflect clinical benefit such that it can be used as the primary clinical outcome endpoint in a similar study that is double-blinded, by assessment of the relationship of the scale to changes in clinical and symptom outcomes, including time to clinical recovery, occurrence of fever, cough, dyspnea, reduction in oxygen requirements, and other measures.
- To explore the clinical effect of favipiravir + SOC vs SOC as measured by the National Early Warning Score 2 (NEWS2) system.
- To determine the safety of favipiravir plus SOC compared to SOC alone in this population.
- To explore the pharmacokinetics (PK) of this dose regimen of favipiravir in this subject population.

This statistical analysis plan (SAP) is designed to outline the methods to be used in the analysis of study data in order to answer the study objective(s). Populations for analysis, data handling rules, statistical methods, and formats for data presentation are provided. The statistical analyses and summary tabulations described in this SAP will provide the basis for the results sections of the clinical study report (CSR) for this trial.

This SAP will also outline any differences in the currently planned analytical objectives relative to those planned in the study protocol.

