## **5. CHANGES TO PLANNED ANALYSES**

The following are changes between the protocol-defined statistical analyses and those presented in this statistical analysis plan:

- The hierarchical testing of the key secondary endpoints has been removed, given that this study is a Proof of Concept study that is not meant to act as a pivotal or confirmatory study for marketing authorization.

All changes from procedures outlined in the protocol and procedures outlined in this SAP will be summarized in the study report. Decisions to deviate from planned analyses will be documented at the time they are made.

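### SAP 4.5.2 omits, undeclared, Protocol 9.7's adverse-event severity table, its discontinuation and death rows, and the between-arm difference in TEAE proportions

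*SAP*

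**What the plan says.** Protocol 9.7 plans TEAE summaries by treatment group, broken down by system organ class and preferred term, severity, relatedness and seriousness. It adds an overview with eight rows: any, related, serious, related serious, leading to discontinuation, related and leading to discontinuation, leading to death, and related and leading to death. For these rows it states: "The difference in proportions between treatment groups in each of these categories will be calculated".

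SAP 4.5.2 keeps the organ-class and preferred-term displays. Its overview covers "The number and percentage of patients with any TEAE, with any TEAE assessed by the Investigator as related to treatment, with any serious TEAE" and, fourth, serious events potentially related to treatment, by arm and overall. Deaths and discontinuations due to adverse events appear in that section only as listings: "By-subject listings also will be provided for the following: subject deaths, SAEs, and AEs leading to treatment/study discontinuation". No table by severity and no between-arm difference is named. SAP 3.3 attaches 90% confidence intervals to category percentages, not to a difference between arms.

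The safety objective in SAP 1.1.2 remains comparative: "To determine the safety of favipiravir plus SOC compared to SOC alone in this population". The same section says that the SAP's analyses and tables are the foundation for the results in the study report, and that the SAP will set out where it departs from the protocol. SAP Section 5 lists one departure: "The hierarchical testing of the key secondary endpoints has been removed".

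**The concern.** The randomized SOC arm is what allows an excess of adverse events on favipiravir to be separated from the illness and its background care. In an open-label trial, the investigator's judgement of relatedness cannot do that job. The protocol planned the corresponding estimate, a difference in proportions. The SAP gives between-arm estimates with 90% intervals for efficacy outcomes, such as the odds ratio for the ordinal scale (4.3.2.1), but none for adverse events. If the study report follows the SAP, readers will see two columns of percentages and no statement of how uncertain the gap between them is. They will also see no by-arm picture of how severe the events were. Protocol 2.7 expects this study to help define the safety profile and to enable use in people who have been exposed but are not yet ill, so the adverse-event comparison is one of its intended products.

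**Working it through.** **1. Arm size.** Protocol 9.2 gives 25 per arm, and that number drives the precision below. For the favipiravir arm, "it is assumed that the median time to clearance for favipiravir would be approximately 4 days". For the control arm, the same section takes it that "the median time for SOC would likely be approximately 11 days". The other inputs are a 15-day observation period and the sentence that begins "Using two-sided alpha of 0.10 and power of 90"%. Assuming exponential times:
- Hazard ratio = 4/11 = 0.364.
- Probability of clearance by Day 15 = 1 − 2^(−15/4) = 0.926 and 1 − 2^(−15/11) = 0.611; mean 0.769.
- Freedman events = (1.645 + 1.282)² × [(1 + 4/11)/(1 − 4/11)]² = 39.3.
- N = 39.3/0.769 = 51.2, or 52. Power at N = 50 is 89.4%.

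Schoenfeld's formula gives 45, with 93.2% power at 50. The stated 50 is sound for viral clearance. It was not chosen for safety.

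**2. Protocol and SAP side by side.**

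| Item in Protocol 9.7 | In SAP 4.5.2 | Elsewhere in SAP |
|---|---|---|
| Any TEAE | n, % by arm; no difference | – |
| Related | n, % by arm; no difference | – |
| Serious | n, % by arm; no difference | – |
| Related serious | n, % by arm; no difference | – |
| Leading to discontinuation | Listing | 4.1: treatment and study discontinuations with reasons, by arm |
| Related, leading to discontinuation | No row | – |
| Leading to death | Listing of deaths | 4.3.2.7: all-cause mortality, adjusted relative risk with 90% CI |
| Related, leading to death | No row | – |
| Table by severity | None | 1.2.6.3: events are graded, but no table is planned |

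The SAP therefore has four of the eight overview rows, no between-arm difference and no severity table.

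**3. Which differences carry information.** Protocol 8.4.3 defines relatedness against the study drug, and the SOC arm receives none. Four rows depend on relatedness (related, related serious, related leading to discontinuation, related leading to death), and one more concerns stopping study drug. In those five rows the SOC entry is essentially zero or undefined, so the difference only restates the favipiravir percentage. That leaves 8 − 5 = 3 informative contrasts: any TEAE, serious TEAE and TEAE leading to death.

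**4. Precision of a restored difference.** The documents give no TEAE rates, so the incidence p, taken as equal in both arms, is an assumption shown over a range. The half-width of the 90% Wald interval is 1.645 × √(2p(1 − p)/25):
- p = 10%: 1.645 × √0.0072 = 14.0 points
- p = 20%: 1.645 × √0.0128 = 18.6 points
- p = 40%: 1.645 × √0.0192 = 22.8 points

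Two hypothetical results, using the Newcombe 90% interval:
- 10/25 v. 5/25: difference 20 points, interval −1.3 to 39.1
- 5/25 v. 2/25: difference 12 points, interval −4.8 to 28.6

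Power to detect a 20-point excess at two-sided 0.10 with 25 per arm is 55%, 46%, 42% and 41% for SOC rates of 10%, 20%, 30% and 40%.

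**The case against.** The strongest defence is that little is lost. TEAE counts and percentages remain by arm, with 90% intervals if SAP 3.3 is applied to them, so anyone can subtract to get the point difference. Laboratory shift tables and vital signs are also by arm. Mortality has a formal between-arm estimate, and Protocol 8.4.5 records every death as a serious adverse event. Disposition tables show discontinuations and reasons by arm. The study is exploratory, with about 50 subjects, and Protocol 9.7 asks only that differences be calculated: it names no interval and no method. SAP Section 5 also says that changes will be summarized in the study report.

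Most of this stands, and it rules out three stronger readings:
- A reader might infer that the SAP has no comparative adverse-event analysis at all. The by-arm tables, the mortality analysis and the disposition table contradict that.
- A reader might infer that eight useful contrasts were lost. Five mean little in an arm that receives no study drug.
- A reader might argue that comparing the two arms' separate intervals by eye applies a stricter test than the planned 0.10. Neither document plans an adverse-event test. SAP 3.3 confines formal testing to efficacy endpoints, so there is no test level to distort.

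Two things are not answered. The uncertainty of the difference cannot be read from the planned tables, and the severity table has no substitute. Nor does the one declared change, with its rationale about proof of concept, extend to safety. The omission is by silence and not by explicit deletion, but the SAP makes its own tables the foundation of the report.

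**Conclusion.** The point holds as an undeclared narrowing of the safety analysis. SAP 4.5.2 lacks the by-arm severity table, the overview rows for TEAEs leading to discontinuation and to death, and any between-arm difference in TEAE proportions, all of which Protocol 9.7 promised. The practical loss is a between-arm adverse-event estimate with its uncertainty for three informative categories, plus the severity summary.

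Restoring these would not make safety a powered comparison. At 25 per arm the 90% half-width is about 14 to 23 points over the assumed 10% to 40% incidence range. An interval that wide still tells the reader how little the trial can exclude. This is a low-cost improvement that should be made; it does not threaten the trial's main conclusion. It rests on reading the SAP's silence as meaning that the items are not planned, which SAP 1.1.2 supports.

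**What to change.** In SAP 4.5.2:
- Restore the TEAE table by severity and arm. Name the scale, because Protocol 8.4 refers to CTCAE version 5.0 while Protocol 8.4.3 defines mild, moderate and severe.
- Restore the rows for TEAEs leading to death and TEAEs leading to study drug discontinuation. Replace Protocol 9.7's reference to an infusion, since Protocol 6.3 describes tablets.
- For any TEAE, serious TEAE and TEAE leading to death, report the difference in proportions (favipiravir + SOC minus SOC) with a two-sided 90% interval by a small-sample method such as Miettinen-Nurminen or Newcombe. The interval goes beyond Protocol 9.7, and 90% matches SAP 3.3. State that these are estimates, not tests.
- Show the treatment-related and study-drug-discontinuation rows descriptively, without a contrast.
- A difference for diarrhea, which Protocol 2.3 names among the most common events, is optional.

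In SAP Section 5, declare and justify any Protocol 9.7 item that is dropped on purpose.

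The cost is SAP wording, one extra table, two extra rows and a difference column. Protocol 8.4.3 already requires severity, seriousness, relatedness, outcome and withdrawal due to the event to be recorded, so no new data are needed.

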#### 4.5.3. Laboratory Data

Clinical laboratory values will be expressed in SI units.

All laboratory data will be provided in data listings.

Abnormal clinical laboratory values that are clinically significant will be graded according to the CTCAE version 5.0. A listing of all abnormal laboratory values will be provided.

Shift tables for hematology and chemistry parameters from baseline to worst value will be provided by treatment group and overall. All unscheduled visits, if any, will contribute to the last or worst value.

#### 4.5.4. Vital Signs and Physical Examination

The actual values and changes from baseline to each on-study evaluation will be summarized for vital signs by treatment group and overall.

Vital sign measurements will be presented for each subject in a data listing.

#### 4.5.5. Prior and Concomitant Medications

Prior and concomitant medications will be coded using the WHO Drug Dictionary.

The use of prior and concomitant medications will be included in a by-subject data listing.

## **5. CHANGES TO PLANNED ANALYSES**

The following are changes between the protocol-defined statistical analyses and those presented in this statistical analysis plan:

- The hierarchical testing of the key secondary endpoints has been removed, given that this study is a Proof of Concept study that is not meant to act as a pivotal or confirmatory study for marketing authorization.

All changes from procedures outlined in the protocol and procedures outlined in this SAP will be summarized in the study report. Decisions to deviate from planned analyses will be documented at the time they are made.

